1.2. Study Design

Overview of Study Design and Key Features					
Visit 0* Discussion of informed consent.	Visit 1 Sequence Arm	Visit 1 Pts receives 1st DPI (as per sequence A, B, C or D) Assessed for errors (critical and overall) after: • Reading the PIL • Then up to 3X instruction from HCP as needed Assessed for teaching and training time to use correctly Participant completes 'Ease of Use' questionnaire Asked willingness to continue with inhaler question ELLIPTA ELLIPTA BREEZHALER BREEZHALER	Up to 30 min break	Visit 1 Pts receives 2nd DPI (as per sequence A, B, C or D) Assessed for errors (critical and overall) after: • Reading the PIL • Then up to 3X instruction from HCP as needed Assessed for teaching and training time to use correctly Participant completes 'Ease of Use' questionnaire Asked willingness to continue with inhaler question BREEZHALER BREEZHALER ELLIPTA ELLIPTA	Up to 30 min break

Signed ICF followed by pts screened for inclusion
 
Visit 1* Pts randomised to 1 of 4 sequences (A, B, C D) and to preference questionnaire & Ease of Use versions
 
<small>*V0 ample time is provided for informed consent discussions. If participant is happy to proceed, they sign the informed consent form and then will be screened. V0 can take place on the same day as V1 where participants are randomised to one of 4 treatment sequences. V1 should be completed no later than 30 days after V0</small>
					
Design Features	
 This is a randomized, multi-centre, open label, placebo inhaler-handling study with a 2x2 complete block crossover design to study critical errors, overall errors, training/teaching time, ease-of-use and willingness to continue and preference attributes of two dry powder inhalers: ELLIPTA and BREEZHALER. Each participant will be randomized to one of the four groups: ELLIPTA followed by BREEZHALER or BREEZHALER followed by ELLIPTA and further refined by assignment of the preference questionnaire version (i.e. version 1 or 2). The study involves two visits which can be completed on the same day. Visit 1 may be completed up to 30 days after visit 0. A participant is considered to have completed study treatment if demonstration of both inhalers has been completed on Day 1 (Visit 1). A participant is considered to have completed the study if all assessments have been completed on Day 1 (Visit 1). Period 1 is complete once demonstration has been completed on the first inhaler after reading the PIL (or receiving up to 3 further HCP instructions), after completing the "Ease of Use" questionnaire and after completing the "Willingness to Continue" question. Period 2 is complete once demonstration has been completed on the second inhaler after reading the PIL (or receiving up to 3 further HCP instructions), after completing the "Ease of Use" questionnaire and after completing the "Willingness to Continue" question. Participants may take up to a 30-minute break between period 1 and period 2. 				

Overview of Study Design and Key Features	
	
 Participants may take up to a 30-minute break after period 2 prior to completion of the preference questionnaire. A participant may withdraw from the study at any time at his/her own request or may be withdrawn at any time at the discretion of the investigator for safety, behavioural, or compliance reasons.
Study intervention	
 This is a placebo inhaler device study. Participants will receive both inhalers (ELLIPTA and BREEZHALER) on day 1 (Visit 1). Discontinuation of study intervention corresponds to withdrawal from the study since each inhaler is only available on a single day. If a participant withdraws during the interval between screening (V0) and Visit 1, there are no assessments that would need to be completed following withdrawal. A participant can also withdraw following randomization. In such cases, the participant may be asked to provide the reason for discontinuation which needs to be documented.
Study intervention Assignment	
 This study will randomly assign 114 adult asthma participants aged ≥ 18 years with mild to moderate asthma, naïve to both DPI inhalers (ELLIPTA and BREEZHALER). Each participant will be randomized to inhaler sequence (ELLIPTA/BREEZHALER or BREEZHALER/ELLIPTA) and to the preference questionnaire (version 1 or version 2). There will be a total of four possible groups: 
 ELLIPTA/BREEZHALER/preference questionnaire version 1 ELLIPTA/BREEZHALER/preference questionnaire version 2 BREEZHALER/ELLIPTA/preference questionnaire version 1 BREEZHALER/ELLIPTA/preference questionnaire version 2 The randomisation schedule will be generated using the GSK validated randomisation software RandAll NG. Eligible participants will be assigned to study treatment randomly using RAMOS NG, an Interactive Web Response System (IWRS).
Interim Analysis	No interim analysis of data is planned for this study.

2. STATISTICAL HYPOTHESES

The primary purpose of this study is to assess the number of critical errors (defined as an error that is most likely to result in no or significantly reduced medication being inhaled) made by asthma participants, after they have read the patient information leaflet(s) (PIL) for each inhaler. This is a superiority study.

The primary estimand is the odds ratio between the ELLIPTA and BREEZHALER inhaler in participants with mild to moderate asthma who make at least one critical error while demonstrating use of the inhaler after reading the PIL(s) based on participants who were able to attempt to demonstrate the use of both inhalers.

The null hypothesis is that there is no difference in the proportion of participants who make at least one critical error on the ELLIPTA inhaler compared with the BREEZHALER inhaler:

$$H_0: P_{\text{ELLIPTA}} = P_{\text{BREEZHALER}}$$

The alternative hypothesis is that there is a difference in the proportion of participants who make at least one critical error on the ELLIPTA inhaler compared with the BREEZHALER inhaler:

$$H_1: P_{\text{ELLIPTA}} \neq P_{\text{BREEZHALER}}$$

This comparison will be tested at the two-sided 5% significance level.

2.1. Multiplicity Adjustment

No multiplicity adjustments will be made for this study.

3. ANALYSIS SETS

Analysis Set	Definition / Criteria	Analyses Evaluated
Screened	
 • All participants who were screened for eligibility and signed the ICF. 	
 • Screening status and reasons for screen failures
Enrolled	
 • All participants enrolled and for whom a record exists on the study database. 	
 • Study population
Randomised	
 • All participants who were randomly assigned to study intervention in the study. • Any participant who receives a randomisation number will be considered to have been randomised. 	
 • Study population
Full Analysis Set (FAS)	
 • All randomised participants who used at least one study inhaler. • Data will be reported according to the randomised study intervention. 	
 • Study population • Safety
Safety	
 • All randomised participants who used at least one study inhaler. • Data will be reported according to the study intervention actually received. 	
 • Safety
Modified intention-to-treat (mITT)	
 • All participants who were randomised to study intervention in the study, completed reading of the PIL and attempted demonstration of both inhalers. • Data will be reported according to the randomised study intervention. 	
 • Efficacy

For CDISC purposes, the modified intention-to-treat (mITT) analysis set refers to the performance evaluable analysis set as defined within the protocol.

4. STATISTICAL ANALYSES

4.1. General Considerations

4.1.1. General Methodology

The full analysis set (FAS) will be used for all Study Population analyses and Safety analyses, the mITT analysis set will be used for all Efficacy analyses and the Safety analysis set will be used to summarise Adverse Device Effects and Serious Adverse Device Effects.

Confidence intervals will use 95% confidence levels unless otherwise specified.

Unless otherwise specified, continuous data will be summarized using descriptive statistics: n, mean, standard deviation (SD), median, minimum and maximum. Categorical data will be summarized as the number and percentage of participants in each category.

4.1.2. Baseline Definition

Baseline is defined as the latest non-missing measurement collected prior to demonstrating inhaler use on the first inhaler (i.e. before period 1). This will generally be on the beginning of the Day 1 (Visit 1) assessment.

Unless otherwise stated, if baseline data is missing no derivation will be performed and baseline will be set to missing.

4.1.2.1. Time taken to demonstrate correct use of the inhaler

Time taken to correctly use each inhaler within the respective period (1 and 2) will be recorded as follows:

- T0: the time taken from when the participant starts to read the relevant sections of the PIL until they complete the reading and are ready to start demonstration of the inhaler.
- T1: the time from when the participant starts the demonstration of the inhaler after reading the PIL until they have completed demonstration of inhaler use.
- T2: the time from when the investigator starts to instruct the participant until correct use is demonstrated (up to a maximum of 3 attempts).
 - T2 includes the time used by the investigator for re-instructing the participants throughout.
 - Note, where correct use of the inhaler is not demonstrated after the fourth attempt, T2 will be calculated from when the investigator starts to instruct the participant until the fourth attempt has been completed.
- T1 + T2: the time from when the participant starts the demonstration until correct use is demonstrated (a total of 4 attempts - once after the reading the PIL and following instruction from investigator up to 3 times).

4.2. Primary Endpoint Analyses

4.2.1. Definition of endpoint

The primary endpoint is participants who make at least one critical error after reading the section on inhaler use in the patient information leaflets (PILs).

4.2.2. Main analytical approach

Comparisons made between the ELLIPTA and BREEZHALER inhaler will be based on those who fall in the S₀₀ stratum. For the full definition of the primary estimand, see section 1.1.

The comparison of ELLIPTA with BREEZHALER will be summarized by an odds ratio. The proportion of participants who make at least one critical error in each inhaler will be analysed using an exact conditional logistic regression model with participant as fixed strata with inhaler, and period as fixed effects. To account for very small or zero frequency counts, an exact test has been specified. In case of period effects, period has been included in the model as a fixed effect (Mehta, et al., 1995). The odds ratio of ELLIPTA relative to BREEZHALER together with the 95% confidence interval and two-sided p-value will also be presented.

Superiority will be declared based on a significance level at the two-sided 5% level.

Residual vs. Fitted plots will be generated to help assess the constant variance assumption. Deviance and Pearson goodness of fit statistics from the model will be examined to help assess the null hypothesis that the model is an adequate fit to the data.

4.2.3. Sensitivity analyses

The analysis for the primary estimand incorporates covariates that are time varying; a feature of a conditional logistic model. Therefore, a sensitivity analysis for the primary estimand will be performed including age and sex as additional baseline covariates.

A sensitivity analysis will be performed using a generalised mixed effects model with a binomial family and log link with a random effect for participant ID and inhaler, period, age and sex as fixed effects. An unstructured variance-covariance matrix will be used. Residual vs. Fitted plots will be generated to help assess the constant variance assumption.

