1.1.2. Estimands

The primary estimand is the odds ratio between the ELLIPTA inhaler and the BREEZHALER inhaler in participants with mild to moderate asthma who make at least one critical error while demonstrating use of the inhaler after reading the PIL(s) based on participants who were able to attempt to demonstrate the use of both inhalers.

The primary estimand consists of the following attributes:

- *Inhaler comparison*: ELLIPTA or BREEZHALER inhaler.
- *Population*: participants with mild to moderate asthma diagnosis who attempt demonstration of both inhalers.
- *Variable*: participants who make at least one critical error after reading the section on inhaler use in the PIL (without further instruction).

- *Population-summary measure*: The odds ratio between the ELLIPTA and BREEZHALER inhalers.
- *Intercurrent event*: Not attempting demonstration of the inhaler (ELLIPTA or BREEZHALER). This is addressed in the population attribute (principal stratum strategy).

A principal stratum strategy will be used to address the intercurrent event for participants who do not attempt demonstration of the inhaler (ELLIPTA or BREEZHALER). This means all participants randomized will fall into exactly one of the following four strata:

1. S_{00} : Stratum of randomized participants who attempt inhaler demonstration (ELLIPTA and BREEZHALER) independent of period.
2. S_{01} : Stratum of randomized participants who attempt the demonstration of the BREEZHALER inhaler and do not attempt demonstration of the ELLIPTA inhaler independent of period.
3. S_{10} : Stratum of randomized participants who attempt the demonstration of the ELLIPTA inhaler and do not complete demonstration of the BREEZHALER inhaler independent of period.
4. S_{11} : Stratum of randomized participants who do not attempt inhaler demonstration (ELLIPTA and BREEZHALER) independent of period.

Comparisons made between the ELLIPTA and BREEZHALER inhaler will be based on those who fall in the S_{00} stratum.

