All secondary estimands will use the same population, inhaler comparison and strategy for the intercurrent event as for the primary estimand. Secondary estimands for the proportion of participants who still make at least one critical error after receiving further HCP instruction, the proportion of participants who make at least one overall error after reading the PIL(s) and the proportion of participants who make at least one overall error after receiving further HCP instruction will use the same summary measure as for the primary estimand. Training/teaching time will be summarized using median time for each inhaler.

Each study primary and secondary objective is presented in [Table 2](#) with additional information, including pre-specified estimands with related attributes.

Table 2 Estimands

The following two attributes apply to all estimands listed in the table below:

- Inhaler comparison: ELLIPTA inhaler vs BREEZHALER inhaler
- Population: participants with mild to moderate asthma diagnosis who attempt demonstration of both inhalers (principal stratum strategy).

Objective	Estimand Category	Estimand	Intercurrent Event Strategy	Population Level Summary Measure
		Variable/Endpoint		
Primary Objective: To compare the proportion of participants who make at least one critical error after reading the section on inhaler use in the patient information leaflets (PILs) for ELLIPTA and BREEZHALER inhalers.	Primary	Participants who make at least one critical error after reading the section on inhaler use in the patient information leaflets (PILs).	Not attempting demonstration of the inhaler (ELLIPTA or BREEZHALER).	Odds ratio between ELLIPTA and BREEZHALER.
	Sensitivity		As for primary.	As for primary.
Secondary Objective: To compare the proportion of participants who still make at least one critical error after receiving further instruction (up to 3) from the HCP.	Secondary 1	Participants who still make at least one critical error after receiving further instruction (up to 3) from the HCP.	As for primary.	As for primary.

Objective	Estimand Category	Estimand		
		Variable/ Endpoint	Intercurrent Event Strategy	Population Level Summary Measure
Healthcare Professional (HCP) for ELLIPTA and BREEZHALER inhalers				

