5. SAMPLE SIZE DETERMINATION

A total of 114 participants will be randomly assigned to study intervention such that approximately 114 evaluable participants complete the study.

The sample size for a 2x2 crossover study is based on the formula presented by (Chow, 2008) and (Lui, 2016). To calculate the conditional odds ratio (via McNemar's) the proportion of participants who have discordant pairs (those who had at least one critical error in one inhaler but not the other) was determined based on expert advice. A panel of 5 experts was convened to consider the evidence from previous studies of similar design [(van der Palen J, 2016), (van der Palen J, 2018)] and with consideration given to observational studies in the literature [(Khassawneh BY, 2008), (Melani AS, 2011), (Arora P, 2014), (Chorão P, 2014), (Takaku Y, 2017), (Ocakli B, 2018)]. A consensus view of the likely error rates that would be observed with the ELLIPTA and BREEZHALER devices was subsequently reached.

A consensus was reached that the proportion of participants who make a critical error in the ELLIPTA inhaler and not on the BREEZHALER inhaler would be 6% and the proportion of patients who make a critical error in the BREEZHALER inhaler and not on the ELLIPTA inhaler would be 20%.

Based on the discordant proportions, an odds ratio of 0.3 was calculated and a standard deviation on the log odds ratio scale of 2.785 was calculated based on GSK study 200301 (van der Palen J, 2016). Based on these estimates and a two-sided Type I error rate of 5%, a total of 114 participants are required to provide 90% power. No withdrawals are expected based on previous similarly designed studies. No correlation between periods is assumed and no carry over effect is assumed based on previous evidence (van der Palen J, 2013). Moreover, both inhalers will contain placebo and participants may have up to a 30-minute break after demonstrating the first inhaler.

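### The sensitivity analysis of the primary odds ratio is specified with a log link, so it would estimate a risk ratio

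*SAP*

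**What the plan says.** The primary estimand's summary measure is "The odds ratio between the ELLIPTA and BREEZHALER inhalers" (SAP 1.1.2), and the Primary row of SAP Table 2 repeats it. SAP 4.2.2 estimates it from data "analysed using an exact conditional logistic regression model with participant as fixed strata with inhaler, and period as fixed effects".

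SAP 4.2.3 explains that conditional logistic regression uses only covariates that vary within a participant, and therefore "a sensitivity analysis for the primary estimand will be performed including age and sex as additional baseline covariates". The model it then specifies is a "generalised mixed effects model with a binomial family and log link with a random effect for participant ID", with inhaler, period, age and sex as fixed effects and an unstructured variance-covariance matrix. Protocol 9.4.1 specifies the same model. In SAP Table 2 the Sensitivity row gives the population-level summary measure as "As for primary".

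The list of changes from the protocol (SAP 4.7, Table 3) contains only the renaming of an analysis set. Neither document mentions a risk ratio or a step that turns the log-link result into an odds ratio.

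**The concern.** A log link models the logarithm of the error probability, so the exponentiated inhaler coefficient is a ratio of probabilities. An odds ratio requires the logit link. SAP Table 2 and SAP 4.2.3 therefore cannot both be followed as written.

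The only stated reason for the second model is to add age and sex. As specified, the effect scale changes along with the covariates. A gap between the primary and sensitivity estimates would then be partly, or wholly, the change of scale. With non-negative correlation within participants the risk ratio lies closer to 1, so a reader could take the gap for attenuation after adjustment. An output that follows Table 2 would also label a risk ratio as an odds ratio.

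**Working it through.** **Inputs**
- Critical error on ELLIPTA only: 6%. On BREEZHALER only: 20% (protocol 9.2, SAP 5).
- N = 114, planned odds ratio 0.3, SD 2.785 on the log odds ratio scale, two-sided 5%, 90% power (same sections).
- Share erring on both inhalers, *c*: not given. SAP 5 does say "No correlation between periods is assumed and no carry over effect is assumed", which fixes one value of *c*. Other values below are assumptions.

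**The plan's own figures reproduce**
- Conditional odds ratio = 0.06 / 0.20 = 0.30.
- Participants per sequence = (1.960 + 1.282)² × 2.785² / (ln 0.30)² = 56.2, rounded up to 57, so 114 in total. The sensitivity model plays no part in this.

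**Value of *c* with no correlation between periods**
- Solve *c* = (*c* + 0.06)(*c* + 0.20), which gives *c* = 0.0166.
- Error proportions are then 0.0766 on ELLIPTA and 0.2166 on BREEZHALER.
- Risk ratio = 0.0766 / 0.2166 = 0.354. The conditional odds ratio stays at 0.30.

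**Fit of both links**

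A random-intercept binomial model with an inhaler effect was fitted by maximum likelihood to the expected paired table: both *c*, ELLIPTA only 0.06, BREEZHALER only 0.20, neither 0.74 − *c*. Period, age and sex effects were set to zero. With a log link and a normal random intercept, fitted probabilities can exceed 1, so they were capped at 1. The simple ratio of error proportions, (0.06 + *c*)/(0.20 + *c*), needs no cap and is shown beside the fit.

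| Share erring on both, *c* | Logit link, exp(b) | Log link, exp(b), capped | Simple risk ratio |
|---|---|---|---|
| 1.7% (no correlation) | 0.30 | 0.35 | 0.35 |
| 5% (assumed) | 0.30 | 0.42 | 0.44 |
| 10% (assumed) | 0.30 | 0.47 | 0.53 |
| 20% (assumed) | 0.30 | 0.51 | 0.65 |
| 30% (assumed) | 0.30 | 0.54 | 0.72 |

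The fitted log-link value is 1.2 times the odds ratio at 1.7% (0.354/0.30) and 1.4 to 1.8 times at 5% to 30% (0.425/0.30 and 0.540/0.30). The logit model returns 0.30 as long as the within-participant correlation is not negative. At *c* = 0, where it is negative, the logit link gives 0.255 and the log link 0.300.

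**Approximate Wald 95% intervals at N = 114, no correlation**
- Odds ratio: expected discordant counts are 114 × 0.06 = 6.84 and 114 × 0.20 = 22.8. SE(log OR) = √(1/6.84 + 1/22.8) = 0.436, so the interval is 0.13 to 0.71.
- Risk ratio: expected error counts are 114 × 0.0766 = 8.73 and 114 × 0.2166 = 24.69. SE(log RR) = √(0.9234/8.73 + 0.7834/24.69) = 0.371, so the interval is 0.17 to 0.73.

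**The case against.** The strongest case on the other side concerns weight.

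- **Reach.** Superiority is declared only from the exact conditional model, no decision rule uses the sensitivity model, and log may be a slip for logit. The limited reach is accepted. But the same wording stands in both documents and remains in SAP version 2, and a programmer working literally would fit a log link.
- **Size.** The both-error share is not in the plan. Under its own no-correlation assumption the gap is only 0.30 against 0.35, and the intervals nearly coincide. That is the one figure tied to the plan; the larger gaps are conditional on assumed shares. The mismatch of scale exists at every share.
- **The cap.** At shares of 5%, 10%, 20% and 30%, about 2%, 7%, 17% and 26% of participants have a BREEZHALER probability at the cap, so the fitted coefficient is no longer exactly the risk ratio of the table. This is correct, but the simple risk ratios are further from 0.30, so the cap understates the gap.
- **The matrix.** If the unstructured matrix were a 2×2 residual covariance in a marginal model, a logit link would give a population-averaged odds ratio: 0.37, 0.44, 0.53 and 0.56 at 5%, 10%, 20% and 30%. The text names a participant random effect, so the participant-specific reading is the natural one. The point does show why the phrase should be settled in the same edit.
- **Displays.** SAP section 1 leaves output details to a separate specification, and an odds ratio could be computed from fitted log-link probabilities. Mislabelled output is therefore a risk, not a certainty. The plan provides for no such conversion.

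**Conclusion.** The concern holds. Read literally, the protocol and SAP produce a risk ratio from an analysis whose declared summary measure is an odds ratio, and nothing in either document reconciles the two. The sensitivity model can still confirm direction and significance with age and sex added, because a risk ratio of 1 and an odds ratio of 1 are the same null. It cannot confirm the magnitude or interval of the primary odds ratio on a common scale.

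The plan-based size is a factor of 1.2; factors of 1.4 to 1.8 depend on assumed both-error shares of 5% to 30% and on the capped fit with no period, age or sex effects. This should be corrected, but it does not threaten the primary conclusion.

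**What to change.** In protocol 9.4.1 and SAP 4.2.3, replace the log link with a logit link. The model with age and sex then gives a participant-specific odds ratio comparable with the conditional one. In the same edit, state which matrix is unstructured. If the only random effect is a single participant intercept, it has one variance and the phrase can be dropped.

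If a risk ratio is what the sponsor wants, keep the log link, label the result as a risk ratio, and amend the summary measure in the Sensitivity row of SAP Table 2.

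The cost is one word in each document and one clarified sentence. Data collection, sample size, significance level and the primary model do not change.
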